3.2.4 Baseline Value

The baseline value will be defined as the assessment collected at the Baseline Visit or the first available record starting with the admission day.

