5.0 ANALYSIS OF PARTICIPANT BASELINE CHARACTERISTICS

Baseline demographics and characteristics including sex (at birth) (DEM), age, ethnicity, race, education level, marital status, and employment will be summarized by site and induction procedure for the ITT population. The following additional important baseline characteristics will also be summarized by site and induction procedure: gender and sexual orientation (S97), homelessness status (NMS), first COWS score recorded on Day 1 of admission (COW), history of overdose (ODQ), number of days since last self-reported opioid use at Day 1 of admission (TAP), baseline substance use (UDS and TLFB), medical and psychiatric history (MHX), baseline mental health screening: Adult ADHD Self-Report Screening Scale for DSM-5 (Score \geq 14) (AAS), PTSD Checklist for DSM-5 (Score \geq 31) (PCL), Generalized Anxiety Disorder (Score \geq 8) (GA7), Patient Health Questionnaire (PHQ-9) (Score \geq 10), criminal history (NMS), health insurance/care plan (NMS), history of medication for opioid use disorder (NMS), number of times attempted and completed opioid detoxification (MHX) and previous unsuccessful inductions onto XR-NTX (MHX). Age will be summarized as a continuous and categorial variable. A summary of baseline demographics and characteristics will also be presented for study completers. If differences between induction procedures are suspected, statistical testing may be performed.

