8.4 Definition of the Secondary Outcome Measures

Key secondary analyses to be conducted by the DSC:

A key secondary objective is to summarize the below outcome to confirm expected characteristics of the RP compared to SP:

1. The time to receipt of first injection of XR-NTX as measured by the number of days from admission to first XR-NTX injection. This will be conducted on the successfully inducted population only. Day of admission is defined as Day 1 (E97ADMDT) as recorded on the ENRC or ENRD forms, and day of first XR-NTX injection (EOIINJDT) is captured on the End of Induction form (EOI). It will be calculated as Date of injection (EOI.EOIINJDT) – Date of admission (ENRC/ENRD.E97ADMDT) +1.

Additional key secondary objectives are to compare the below outcomes of RP versus SP for all enrolled participants (ITT population).

2. Craving for opioids measured by Visual Analog Scales (VAS) as captured daily on the self-reported inpatient opioid craving form (OCI) during induction phase. The OCI form collects intensity of craving both at time of assessment and within the last 24 hours prior to assessment. If either measurement is collected multiple times on the same assessment date, the average measurement will be used for analysis.
3. Opioid withdrawal symptoms as measured by the Subjective Opioid Withdrawal Scale (SOWS) and the Clinical Opiate Withdrawal Scale (COWS). SOWS is captured on the SBW form at baseline and daily during induction phase. COWS is captured on the COW

form starting with day of admission and daily during the induction phase leading to the first XR-NTX injection. Note that during induction, COWS may be measured multiple times per day while SOWS is expected to be assessed only once per day. If multiple SOWS measures are collected on the same assessment date, the average measurement will be used for analysis. If multiple COWS measures are collected on the same assessment, the peak measurement will be used.

4. Retention in the trial to receive at least one XR-NTX injection after the first injection as captured on the XR-NTX Administration (INN) form.
5. Safety, as measured by targeted safety events, overdoses, and serious adverse events related to study medication during the induction phase and during eight weeks of post-induction. Detail on safety outcome analysis is provided in Section 9.0.

Other secondary analyses to be conducted by LN:

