8.5 Analyses of the Key Secondary Outcome Measures

The key secondary outcome, days to first injection, will be summarized by induction procedure. It will be compared between the two induction procedures in the inducted population using a Cox proportional hazards model. The log hazard rate of receiving the first XR-NTX injection will be modeled as a function of induction procedure (RP vs SP), step and site. The SAS PHREG procedure will be used to estimate the hazard ratio for the induction procedures. The 95% Wald Confidence limits will be estimated.

SAS Code example:

```
proc phreg data=inject;
  class trt step site;
  model time*censor (0) = trt step site;
  hazardratio trt;
run;
```

where:

- time - is the time to event variable, i.e., the days to first injection.
- censor - is the censoring indicator variable. The censoring value (censor=0) means censored. However, given the analysis is conducted in the inducted population only, there will be no censored observations, i.e., censor=1 for all observations.
- trt - is the variable that defines the induction procedure (RP or SP)

- step - is 1 through 5
- site - is the site code for the 6 sites.

The other key secondary outcomes including craving for opioids (VAS) and opioid withdrawal measures (COW and SOW) will be summarized in tabular and graphical form for each day of the induction phase by induction procedure. In the Standard Procedure, scores will be summarized by Buprenorphine Day, Buprenorphine Washout Day, Naltrexone Day, Day of XR-NTX Injection Success or Day of XR-NTX Injection Failure. In the Rapid Procedure, scores will be summarized by Pre-Buprenorphine Day, Buprenorphine Day, Buprenorphine Washout Day, Naltrexone Day, Day of XR-NTX Injection Success or Day of XR-NTX Injection Failure.

Longitudinal opioid craving and withdrawal scores may be analyzed using mixed-effects models adjusting for induction procedure, site, step, and days since admission. The presence of at least one moderate to severe daily COWS score (maximum score ≥ 12) and presence of moderate to severe average daily COWS score (average score ≥ 12) will be analyzed using a mixed-effects model with logit-link function.

SAS code example that may be used to analyze binary COWS outcome:

```
proc glimmix data = secondout method = quad IC=PQ;  
  class patid site trt(ref='SP') step (ref='1');  
  model outcome (event='1')= trt site day step/ dist = binary link = logit solution oddsratio;  

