  random intercept / subject=patid type=ar(1);  
run;
```

where:

- trt - is the variable that defines the induction procedure (RP or SP)
- outcome - is the presence of moderate to severe daily COW score (Yes=1 or No=0)
- step - is 1 through 5
- site - is the site code for the 6 sites.
- day- days since admission to the unit
- patid- participant ID

SAS code example that may be used to analyze continuous SOWS and VAS outcomes:

```
proc mixed data = secondout;  
  class patid site day_cat trt(ref='SP') step (ref='1');  
  model outcome = trt site day step/ solution cl;  
  random intercept / subject = patid;  
  repeated day_cat/ type = AR(1) subject = patid;  
  estimate "trt effect" trt 1 -1;  
run;
```

where:

- trt - is the variable that defines the induction procedure (RP or SP)
- outcome - is either mean SOWS or mean VAS score
- step - is 1 through 5
- site - is the site code for the 6 sites
- day - days since admission to the unit (continuous)
- day_cat- days since admission to the unit (categorical) as required by the repeated statement in the model
- patid- participant ID

Retention in the trial to receive at least one XR-NTX injection after the first inpatient injection as captured on the XR-NTX Administration (INN) form will be analyzed similarly to the primary outcome using a mixed-effects model with logit-link function.

Frequency of targeted safety events, overdose episodes and SAEs by relationship to study medication will be reported. Safety data analysis is provided in detail in Section 9.0.

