	Gibson Recovery Center (N=XX)	Nexus Recovery Center (N=XX)	Stony Brook Eastern Long Island Hospital (N=XX)	Aspire Health Partners (N=XX)	Avery Road Treatment Center (N=XX)	ADAPT (N=XX)	Total (N=XX)
Gay or lesbian							
Bisexual							
Queer							
Not sure							
Something else							
Employment							
Working now	N (X.x%)						
Only temporarily laid off, sick leave, or maternity leave							
Looking for work, unemployed							
Retired							
Disabled permanently or temporarily							
Keeping house							
Student							
Other							
Location participant spent the night before coming to the unit							
Missing	N (X.x%)						
Own apartment, room or house - subsidized, for example Section 8 or living in public housing							
Own apartment, room or house - not subsidized							
Someone else's apartment, room or house							

Table 16: Summary of Baseline Characteristics by Site

	Gibson Recovery Center (N=XX)	Nexus Recovery Center (N=XX)	Stony Brook Eastern Long Island Hospital (N=XX)	Aspire Health Partners (N=XX)	Avery Road Treatment Center (N=XX)	ADAPT (N=XX)	Total (N=XX)
Hotel, SRO, or boarding home							
Halfway house, residential treatment program (focus: establishing sobriety)							
Transitional housing (focus: movement into permanent housing)							
Institution (hospital, nursing home, etc.)							
Homeless shelter							
Outdoors/street, abandoned/public building, vehicle, or other place not meant for human habitation							
Detox							
Other - homeless							
Other - stable housing							
Other							
Refused							
First COWS Score on Day 1 of admission							
N	N						
Mean	x.x						
SD	x.xx						
Minimum	x						
25th Percentile	x.x						
Median	x.x						
75th Percentile	x.x						
Maximum	x						

Table 16: Summary of Baseline Characteristics by Site

	Gibson Recovery Center (N=XX)	Nexus Recovery Center (N=XX)	Stony Brook Eastern Long Island Hospital (N=XX)	Aspire Health Partners (N=XX)	Avery Road Treatment Center (N=XX)	ADAPT (N=XX)	Total (N=XX)
History of lifetime opioid overdose	N (X.x%)						
Number of lifetime overdoses							
N	N						
Mean	x.x						
SD	x.xx						
Minimum	x						
25th Percentile	x.x						
Median	x.x						
75th Percentile	x.x						
Maximum	x						
Number of days since last self-reported opioid use at Day 1 of admission							
N	N						
Mean	x.x						
SD	x.xx						
Minimum	x						
25th Percentile	x.x						
Median	x.x						
75th Percentile	x.x						
Maximum	x						
Baseline substance use (Urine Drug Screen)							

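### The SAP 8.5 withdrawal and craving models omit admission severity, although a first Day 1 COWS is collected before the two regimens diverge

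*SAP*

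**What the plan says.** SAP 8.5 states: "Longitudinal opioid craving and withdrawal scores may be analyzed using mixed-effects models adjusting for induction procedure, site, step, and days since admission". The example code for SOWS and VAS has the model line "model outcome = trt site day step/ solution cl", with a patient random intercept and AR(1) residuals. The example code for binary COWS has "model outcome (event='1')= trt site day step/ dist = binary link = logit solution oddsratio". The result shells, Tables 47 and 48, have rows for Rapid versus Standard, inpatient day and the site contrasts. They have no baseline row, and no row for step although step is in the model.

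Admission severity is recorded. SAP 5.0 lists the first Day 1 COWS among the important baseline characteristics, and the shells in SAP 19.1.2 tabulate it as "First COWS Score on Day 1 of admission". SAP 2.2.2 includes COWS among the forms that may be abstracted retrospectively to Day 1; SOWS and craving are not on that list, although protocol 12.2.2 also provides for chart abstraction of SOWS. On SOWS, SAP 8.4 says: "SOWS is captured on the SBW form at baseline and daily during induction phase". SAP 2.2.2 places baseline assessments anywhere in Days 1 to 4, and SAP 3.2.4 defines the baseline value as the "assessment collected at the Baseline Visit or the first available record starting with the admission day".

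Baseline covariates are planned elsewhere only for the primary outcome: baseline fentanyl, and covariates found unbalanced or prognostic, both in SAP 8.3.

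**The concern.** Withdrawal at admission is a natural predictor of withdrawal and craving over the following days. Omitting a prognostic covariate from a linear model widens the interval for RP versus SP. SAP Table 5 hypothesises comparable craving and withdrawal in the two procedures, so a needlessly wide interval makes a null result easy to read as comparability. Protocol 4.1.2 names more severe precipitated withdrawal as a risk of RP, so these models address its main tolerability question.

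There is also a question of bias. Randomization is by site, the procedure is open-label, and patients may consent up to the fourth day of admission, when the site's current procedure is already under way. If the kind of patient who enrols changes when a site moves from a roughly 13-day to a roughly 6-day regimen, site and step terms will not absorb the change.

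**Working it through.** The documents give no power, SD or correlation for SOWS, VAS or COWS, so there is no stated figure to reproduce.

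**Inputs from the documents.** Six sites, five steps, 15 participants per cell (SAP 12.0); the optimized design matrix (SAP Figure 1); model terms procedure, site, step and day (SAP 8.5).

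**Assumed inputs.** The correlation ρ between Day 1 COWS and a participant's later mean score, conditional on site and step: 0.2 to 0.7. A shift in admission severity at crossover: up to 0.3 SD.

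**Standard error without baseline.** Work with the participant's mean score, unit SD, and fixed site and step. The treatment variation left after removing site and step means is 15 − 5(1² + 0.8² + 0.6² + 0.4² + 0.2²) − 6(1² + 2² + 3² + 4² + 5²)/36 + 30(0.5²) = 15 − 11 − 9.167 + 7.5 = 2.333. Then SE = 1/√(15 × 2.333) = 1/√35 = 0.169 SD.

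**Standard error with baseline.** Multiply by √(1 − ρ²). The inflation from omission is 1/√(1 − ρ²) − 1, and the equivalent loss of participants is 450ρ².

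| ρ | SE with baseline | Inflation if omitted | Equivalent loss of 450 |
|---|---|---|---|
| 0.2 | 0.166 | 2% | 18 |
| 0.3 | 0.161 | 5% | about 40 |
| 0.5 | 0.146 | 15% | about 112 |
| 0.7 | 0.121 | 40% | about 220 |

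**What site and step remove.** On the same matrix, a time trend common to all sites and a fixed difference between sites each contribute 0 to the RP estimate. A shift occurring at every crossover contributes ρ × shift in full. A shift at only one of the four switching sites contributes 0.2 or 0.3 of that: for the second site, (4 × 0.7 − 14/6)/2.333 = 0.2; for the third, (3 × 0.9 − 12/6)/2.333 = 0.3; the fourth and fifth mirror these.

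For a 0.3 SD shift at every crossover, the bias is 0.06 SD at ρ = 0.2, 0.15 SD at 0.5 and 0.21 SD at 0.7. These are 0.35, 0.89 and 1.24 of the unadjusted SE.

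**Simulation check.** Daily series with a patient random intercept were simulated, 60 runs per setting, without the AR(1) residual. With ρ = 0.5, a 0.3 SD shift and a true effect of 0, the mean RP estimate was 0.148 without baseline and 0.010 with it. With no shift, the mean model SE fell from 0.188 to 0.181, 0.168 and 0.146 at ρ = 0.3, 0.5 and 0.7, which is inflation from omission of about 4%, 12% and 29%. These are below the table because ρ in the simulation is the correlation with the participant's underlying level, and daily noise dilutes the correlation with the observed mean.

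**Which baseline value.** SAP Tables 3 and 4 give the same planned Day 1 buprenorphine in both procedures. Under RP, standing clonidine and clonazepam start on Day 2 and oral naltrexone on Day 3. A baseline taken on Days 2 to 4 may therefore be post-treatment. RP also allows adjunctive medication later on Day 1 if needed, so the first score of that day is the safest.

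**The case against.** The strongest reply is that these are modest analyses. SAP 8.5 makes the SOWS and VAS models optional and presents the code as examples; only the binary COWS model is a firm commitment. SAP 11.0 says the key secondary outcomes are not confirmatory. The firm plan for craving and SOWS is daily summaries and figures. An arm-level imbalance would show in the baseline tables and in the Day 1 row of Table 43, and exploratory objective 1 examines baseline features as predictors and moderators. This limits the weight of the point. It does not answer it: none of these items gives a baseline-adjusted RP effect, and an arm-level table does not isolate a change within sites.

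Four stronger readings are tempting and not supported.

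- A reader might infer that the interval narrows for all three outcomes by the same factor. The √(1 − ρ²) factor belongs to the linear SOWS and VAS models. In the logistic COWS models the odds ratio becomes conditional on baseline, and its SE need not fall.
- A reader might infer that a change in case mix passes whole into the RP estimate. It passes as ρ times the shift, and at 0.2 to 0.3 of that if one site alone changes.
- A reader might infer that ρ is high. COWS is clinician-rated while SOWS and craving are self-reported, and a first Day 1 score may precede peak withdrawal.
- A reader might infer that SAP 3.2.4 rules out a Day 1 COWS. It also permits the first record from admission; the difficulty is that it leaves the choice open.

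**Conclusion.** The point stands as a moderate weakness with an inexpensive remedy. The baseline term is absent from the text, the code and the shells, and no other planned analysis supplies it. SAP 12.0 itself assumes that extra covariates in the primary model improve accuracy.

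The size rests on an unknown ρ. The SE penalty in the linear models is 2% to 5% at ρ of 0.2 to 0.3, about 15% at 0.5 and 40% at 0.7. For binary COWS the benefit is mainly power, and it is not quantified here. The bias is conditional on a change in admission severity at crossover. The open-label site-level design makes that possible, but nothing in the documents shows that it happened, so the plan cannot be said to give a biased RP effect on withdrawal or craving.

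**What to change.** In SAP 8.5, add the first Day 1 COWS as a continuous covariate to the SOWS, VAS and COWS models. Name the Day 1 record explicitly instead of the SAP 3.2.4 baseline value, which may come from a Baseline Visit as late as Day 4. In the adjusted COWS model, start the outcome series on Day 2 so that the covariate is not also an outcome. State a simple rule for a missing Day 1 COWS, for example site-mean imputation with a missingness indicator. Add the covariate row to Tables 47 and 48. Keep the currently planned model, on the full series from admission, as a sensitivity analysis.

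The cost is one term in three model statements and no new data collection. The downsides should be stated in the SAP. Starting on Day 2 departs from the COWS series that SAP 8.4 defines from the day of admission, and participants with only Day 1 scores leave the adjusted model. Some Day 1 COWS values will be missing. COWS is only a proxy for baseline SOWS and craving, so the gain for those outcomes may be small.

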8.6 Definition of the Exploratory Outcome Measures

Exploratory objectives include:

1. Explore baseline demographic and clinical features (e.g., the primary opioid of dependence (heroin/fentanyl vs. prescription opioid)) as: a) predictors of induction success, secondary outcomes and retention during the trial (main effect of predictors), and b) as moderators of differential treatment effect (moderator by treatment interaction).
2. Compare duration of inpatient treatment and the associated costs from the time when detoxification is initiated to the time that XR-NTX is administered to permit analyses of economic costs and benefits of the two induction procedures. Also compare duration of inpatient treatment for all patients regardless of whether XR-NTX was initiated, across RP and SP for ITT population. Participants who failed induction will be evaluated to see if they received any other MOUD.
3. Compare RP versus SP for all enrolled participants in terms of time from day of admission to XR-NTX initiation failure (day of discontinuation of detoxification period that resulted in failure to receive first XR-NTX) and reasons for failure.
4. Compare RP versus SP for all enrolled participants in terms of other depressive, anxiety, and subacute withdrawal symptoms as measured by the Patient Health Questionnaire-9 (PHQ-9) and General Anxiety Disorder-7 (GAD-7).
5. Compare RP versus SP use of alcohol and other drugs of abuse (e.g., cocaine, other stimulants, cannabis, benzodiazepines), by self-report and urine drug screens for all enrolled participants.
6. Explore engagement with medical visits and therapy (based on Medical Management Log, Psychosocial Log, XR-NTX Administration Form, TLFB).
7. Compare RP versus SP for all enrolled participants in terms of use of MOUD as measured by patient self-report on Timeline Followback (TLFB).
8. Investigate the percentage of induction failure participants that receive XR-NTX during the course of the study overall and for each induction procedure as measured by patient self-report on Timeline Followback.
9. Compare RP versus SP for percentage of participants inducted on XR-NTX (during both induction and post-induction phases of the trial).

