5.3 Exploratory Objective(s)

1. Explore baseline demographic and clinical features (e.g., the primary opioid of dependence (heroin/fentanyl vs. prescription opioid)) as: a) predictors of induction

success, secondary outcomes and retention during the trial (main effect of predictors), and b) as moderators of differential treatment effect (moderator by treatment interaction).

2. Compare duration of inpatient treatment and the associated costs from the time when detoxification is initiated to the time that XR-NTX is administered to permit analyses of economic costs and benefits of the two treatments.
3. Compare RP versus SP for all enrolled participants in terms of time from day of admission to XR-NTX initiation failure (day of discontinuation of detoxification period that resulted in failure to receive 1st XR-NTX) and reasons for failure.
4. Compare RP versus SP for all enrolled participants in terms of other depressive, anxiety, and subacute withdrawal symptoms as measured by the Patient Health Questionnaire-9 (PHQ-9) and General Anxiety Disorder-7 (GAD-7).
5. Compare RP versus SP use of alcohol and other drugs of abuse (e.g., cocaine, other stimulants, cannabis, benzodiazepines), by self-report and urine drug screens for all enrolled participants.
6. Explore engagement with medical visits and therapy (based on Medical Management Log, Psychosocial Log, XR-NTX Administration Form, TLFB).
7. Compare RP versus SP for all enrolled participants in terms of use of MOUD as measured by patient self-report on Timeline Followback (TLFB).
8. Investigate the percentage of induction failure participants that receive XR-NTX during the course of the study overall and for each treatment arm as measured by patient self-report on Timeline Followback (TLFB).
9. Compare RP versus SP for percentage of participants inducted on XR-NTX (during both induction and post-induction phases of the trial).

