16.1.2 Primary and Secondary Outcomes (Endpoints)

Primary Endpoint: The primary outcome measure is a dichotomous indicator of whether each participant receives the first XR-NTX injection while inpatient or not at the end of the induction period, which is approximately Day 6 in the Rapid Induction Procedure and Day 13 in the Standard Induction Procedure.

Secondary Endpoints: Secondary endpoints include time to first injection or time to failure to receive first injection, receiving 2nd and 3rd monthly injections of naltrexone, opioid withdrawal symptoms, selected opioid and other drug use, adherence to any type of MOUD and adverse events during the induction period and in the month after XR-NTX initiation as discussed in Section 7.2. A set of additional implementation outcome measures, including acceptability and barriers, are detailed in Section 7.3. A preliminary economic analysis that compares cost of both interventions will also be included.

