Under the above assumptions, the null and alternative hypotheses can be stated as follows: In terms of proportions (p):

Null (inferiority of RP to SP): $p(RP) - p(SP) \leq -0.10$

Alternative (non-inferiority of RP to SP under which power was calculated): $p(RP) - p(SP) > 0.15$

In terms of odds ratios (OR):

Null (inferiority of RP to SP): $OR [odds(RP)/odds(SP)] \leq 0.67$

Alternative (non-inferiority of RP to SP under which power was calculated): $OR [odds(RP)/odds(SP)] > 1.91$

Intraclass Correlation Coefficient: The ICC estimate is based on a logistic regression of induction success/failure in CTN-0051 on treatment arm, with a random site effect whose variance is allowed to depend on arm. It is assumed that any extra covariates added to the model will improve

analysis accuracy, implying that current power estimates are conservative. The estimated site standard deviation in the XR-NTX arm from the regression model using data from CTN-0051 is 0.86, leading to an estimated ICC in the SP arm of 0.14 under the generalized mixed model. The ICC represents the correlation between two individuals chosen randomly without replacement from the XR-NTX arm of CTN-0051, given that they come from the same site.

In summary, the assumptions used for the power calculations for this non-inferiority optimized stepped-wedge cluster randomized trial are as follows:

- The projected number of clusters is 6 (sites), that will enroll participants across 5 periods of time, each period 14 weeks long.
- The projected total number of participants enrolled is 450, with 15 participants enrolled per cluster per time period (equal allocation to sites per time period).
- The outcome of interest is a binomial outcome (the participant received or did not receive the first XR-NTX injection).
- The probability of success in the SP arm is 0.55.
- The probability of success in the RP arm is 0.70 (i.e., an effect size of 0.15).
- The margin of non-inferiority is 10%, which corresponds to an odds ratio of 0.67 (based on proportion of success in RP = 0.45 and proportion of successes in SP = 0.55). Refer to Figure 5 for the relationship between non-inferiority margin as a difference in proportions versus non-inferiority margin as an odds ratio.
- Observations are equally correlated within cluster, regardless of time or induction method with a site standard deviation of 0.86. The corresponding ICC in the SP arm based on a logistic regression with random effects is 0.14.

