16.0 UPDATES TO THE STATISTICAL ANALYSIS PLAN

Table 9: SAP Revision History		
SAP Version	Date of Approval	Summary of Changes
1.0	20-DEC-2022	Initial Version
2.0	13-APR-2023	Clarified description of exploratory outcome #7 in Section 2.1.3. Revised Section 5.0 to add summary table of baseline characteristics in study completers and clarify description of summary tables by site and induction procedure.

		Revised definition of exploratory outcome #2 in Section 8.6. Added shells for tables, listing and figures in Appendix in Section 19.1.
--	--	---

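### Costs are defined only up to XR-NTX administration, so induction failures have no cost, although their inpatient duration is now compared in the ITT population

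*SAP*

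**What the plan says.** SAP 8.6 item 2 words the cost comparison this way: "associated costs from the time when detoxification is initiated to the time that XR-NTX is administered to permit analyses of economic costs and benefits". SAP 2.1.3 item 2 uses the same window, and so does Protocol 5.3 item 2: "associated costs from the time when detoxification is initiated to the time that XR-NTX is administered".

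SAP 8.6 then adds two sentences that appear in neither of those places. The first is "Also compare duration of inpatient treatment for all patients regardless of whether XR-NTX was initiated, across RP and SP for ITT population". The second is "Participants who failed induction will be evaluated to see if they received any other MOUD". The revision table in SAP 16.0 dates this change to version 2.0: "Revised definition of exploratory outcome #2 in Section 8.6". The added text names duration and other medication, not costs.

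Item 3 of the same section compares "time from day of admission to XR-NTX initiation failure" between the procedures. Protocol 16.1.2 makes a general promise: "A preliminary economic analysis that compares cost of both interventions will also be included". It gives no population, time window or estimator. SAP 1.0, Table 1, assigns the exploratory outcomes to the lead node.

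**The concern.** The cost window ends at an event that only successes have, and success is the primary outcome. Followed as written, the cost comparison conditions on a post-assignment result that the trial expects to differ by arm.

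The stated aim is the costs and benefits of the two procedures, and the cost of a procedure includes unit days and medication spent on attempts that fail. A programme choosing between SP and RP would want the cost per patient started on each procedure, and the cost per patient who ends up injected. The success-only contrast gives neither. It describes the cost of a stay that succeeds, which largely restates the two schedules.

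The protocol itself presents shorter stays as a reason to adopt RP (sections 4.2 and 7.2.1), so a reader is likely to treat the cost figure as evidence on that point.

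**Working it through.** The documents give no cost, unit cost or failure-day figure, so there is no plan figure on this point to reproduce and no cost can be computed. Inpatient days are used to show how far the choice of population can move the answer.

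**Inputs from the documents**
- SP success rate, SAP 12.0: "The probability of success in the SP arm is 0.55". The RP rate in the same list is 0.70. Both are planning assumptions.
- Scheduled injection day, SAP 12.0: about Day 13 in SP and Day 6 in RP, taken here as inpatient days.
- About 225 participants per procedure (Protocol 8.0), 450 in total.
- The induction phase may last up to 30 days (SAP 3.2.1).

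**Input assumed**
- Mean day of failure, fS in SP and fR in RP. The illustrative range is 3-10 for fS and 3-5 for fR.

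**Participants without a defined cost**
- SP: (1 − 0.55) × 225 = 101.25
- RP: (1 − 0.70) × 225 = 67.5
- Total: 168.75, about 169 of 450 (37.5%)

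**Success-only difference (SP − RP)**
- 13 − 6 = 7.0 days

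**Difference per enrolled participant**
- SP: 0.55 × 13 + 0.45fS = 7.15 + 0.45fS
- RP: 0.70 × 6 + 0.30fR = 4.20 + 0.30fR
- Difference: 2.95 + 0.45fS − 0.30fR
- Lowest corner (fS 3, fR 5): 2.95 + 1.35 − 1.50 = 2.80
- Highest corner (fS 10, fR 3): 2.95 + 4.50 − 0.90 = 6.55
- Middle case (fS 6, fR 4): 2.95 + 2.70 − 1.20 = 4.45

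**Difference per successful induction** (each arm's mean divided by its success rate)
- SP: 13 + (0.45/0.55)fS = 13 + 0.82fS
- RP: 6 + (0.30/0.70)fR = 6 + 0.43fR
- Difference: 7 + 0.82fS − 0.43fR
- The same three cases give 7.3, 13.9 and 10.2

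**When the success-only 7.0 errs in each direction**
- It overstates the per-enrolled difference if 2.95 + 0.45fS − 0.30fR < 7, that is, fS < 9 + 0.67fR. This holds throughout the assumed range. It fails if both failure days are 30, where the difference is 2.95 + 13.50 − 9.00 = 7.45.
- It understates the per-success difference if 0.82fS > 0.43fR, that is, fS above about 0.52fR.
- RP uses more days per enrolled participant than SP only if fR > 9.83 + 1.5fS. For example, fS 1 and fR 13 gives 2.95 + 0.45 − 3.90 = −0.50.

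**The case against.** The best answer is that the resource use of failures is already in the plan. SAP 8.6 compares inpatient duration across the whole ITT population, item 3 compares time to failure, and days per success could be worked out from ITT duration and the success counts. This stands for days. A reader might infer that the plan ignores failures or reports 7 days as its only result; the documents do not support that.

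It does not settle costs, because a day need not cost the same in both arms. Protocol Table 6B has standing adjunctive doses and a naltrexone titration with repeat withdrawal scoring, and section 10.4.4 adds daily counselling. Table 6A has a taper followed by medication as needed.

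A second answer is that Protocol 16.1.2 promises a cost comparison not restricted to successes, and that quality-of-life and service-use forms are scheduled at Weeks 4 and 8, which failures attend. The promise is real, but the only operational definition is the window ending at XR-NTX. The service-use form covers services outside the study and the treatment programme (Protocol 12.7.4), so it does not cost the induction stay.

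A third answer is that the direction of any bias is unknown, because no failure day is documented, induction may run to 30 days, and Protocol 10.5.5 lets the unit stabilise failures on other medication. This stands. Overstatement of the per-patient saving is conditional on when failures occur.

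Finally, SAP 8.6 lists exploratory objectives without analysis methods for any of them. That limits the importance of the point. It does not remove it, because item 2 states a cost window and that window excludes failures.

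**Conclusion.** The gap is real and narrow. Costs, unlike inpatient duration, are not extended to the ITT population, so cost per enrolled participant and cost per successful induction are both undefined. On the planning rates, about 169 of 450 participants have no defined cost; the 45% and 30% are complements of assumptions, not observed shares.

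In days, under the assumed failure days, the success-only 7.0 compares with 2.8-6.6 per enrolled participant and 7.3-13.9 per success. These figures show scale only. They depend on failure days that the documents do not give and carry no prices.

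A reader might go further and infer that the plan cannot show which procedure costs less. The documents do not support that. ITT duration is planned, and across the assumed range RP uses fewer days on all three measures. In days, the sign reverses only if RP failures stay much longer than SP failures. What the population changes here is mainly the size of the difference.

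This is a worthwhile improvement to an exploratory objective. Primary inference is unaffected.

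**What to change.** In SAP 8.6 item 2, state that costs, like duration, are computed for every ITT participant, from admission to the day of XR-NTX or the day of failure recorded on the End of Induction form. Add a sensitivity analysis that runs to unit discharge where that date is available, because SAP 3.2.1 notes that the end of induction and discharge can differ and a failure-day cut-off would miss unit days after a failed attempt.

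Report:
- mean cost per enrolled participant by procedure, with the RP − SP difference adjusted for step and site;
- cost per successful induction, as total arm cost divided by arm successes;
- the success-only figure, kept as descriptive.

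Bring SAP 2.1.3 item 2 and Protocol 5.3 item 2 into line.

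The price is a short text change, one extra table and a failure end point that must be applied consistently. The main window needs no new data collection. Admission dates, End of Induction dates for successes and failures, and daily medication logs to the last induction day are already planned for all enrolled participants (SAP 2.2.2, 3.2 and 6.0). Those logs stop at the end of induction, so the discharge-based analysis may cover unit days better than medication.
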